## Study Population:

The study population consists of a diverse group of Stanford faculty, staff, and students, and the local Santa Clara County community and specific external sources with known positive saliva samples and DUA/MTA in place. More specifically, there are three sub-populations to address our aims:

- 1) (Positive population) Hospitalized patients (N=15)
- 2) (High risk and positive population) People from Bay area community and external sites with known positive saliva samples and DUA/MTA in place; Those with a suspected COVID infection seeking testing within the Stanford Health Care system (N=1500)
- 3) (Low risk population) People from Bay area community; Students on the Stanford campus and employees at Stanford Health Care (N=1500)

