### **Analysis of the Validity Outcomes**

The sensitivity, specificity, positive predictive value (PPV), and negative predictive value (NPV) of the test will be estimated using the results collected in outpatients. The results of the PCR-based test will be the gold standard used to estimate the test's diagnostic accuracy. Home test results will only be included in this analysis if the test is performed within 24 hours of the time the swab used in the PCR tests was collected.

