### **Recruitment:**

The study will recruit up to 3060 participants including 60 hospitalized patients from multiple locations. These will include SHC COVID testing sites, Stanford Health Care

300 and 500P locations (the Emergency Department and other in-patient wards particularly M7, the COVID ward), as well as the front entrance of Stanford hospital and several locations on Campus. We will also be recruiting folks from the bay area community for our study. Participants will fall into two categories: i) those receiving a CLIA certified nasal swab COVID-19 test at SHC at the moment of recruitment, and ii) those not.

We will be recruiting a high-risk population because we will be recruiting from a pool that includes people who are seeking medical attention and/or participating in COVID-related research studies. Feasibility and validity of the tests will be evaluated in the high-risk population. We will be additionally recruiting a low-risk population to assess feasibility in the general population. Hospitalized patients will provide information on concordance between the CLIA COVID test and the home saliva test in patients over a five day period when we expect to see a mix of positive and negative tests.

To increase the number of SARS-CoV-2 positive saliva samples, we will accept deidentified and deactivated saliva samples from external sources, including Guatemala. All of these external sources will have DUA/MTA in place and will have institutional approval and have received written informed consent from all participants for the local trials, including the sharing of these samples with Stanford University for the current trial.

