### *Test description*

[figure not shown]
Test materials: saliva collection tube, small handheld centrifuge, test kit (plasticware) The test kit should be stored in a regular fridge (4C) at the location of the participant - prior to use.

The test materials include a cartridge containing a tube with closed reagents into which the participant will provide the saliva sample. Participants will be asked to provide 1ml of saliva into the collection tube, after which they will close the cap of the cartridge. They will be asked to pour boiling water into a mug and place the tube into the boiling water for 3 minutes. At the end of 3 minutes, they will then place the tube back in the mug of water for 40 minutes. At the end of 40 minutes, they remove the tube and note the color (pink/ orange = negative, yellow = positive). They will take a photograph of the tube against a given white photocard (provided in the kit) and upload it to the website. After filling in the short (<1 minute) symptom questionnaire and the short usability (<20 seconds) questionnaire they will dispose of the tube in the trash.

At that point, **if the test result is negative** (no evidence of infection) then they will be asked to do nothing other than fill in a survey and upload the image of the tube via study app. **If the test result is positive** they will be instructed to behave as if they might be infectious in their home and outside of their home (maximizing the use of masks and distancing) and asked to take a CLIA nasal swab test at their nearest SHC testing site at their earliest opportunity.

Our study provides the option for the participants to take a PCR nasal swab test at Stanford Health Care when their SnapDx tests result or the saliva direct PCR test done by the lab shows a positive SARS-CoV-2 result. Our study will cover the cost of the PCR nasal swab test for the participants.

Figure: Color change in tubes. Yellow color is a positive result

Left sample spiked with random plasmid DNA, right sample spiked with COVID-19 control RNA, at 50 genomes/ $\mu$ L.

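### The 24-hour swab rule lets the SnapDx result itself decide which tests enter the accuracy analysis, and the primary reference and validity population are not fixed

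*Combined protocol and SAP*

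**What the plan says.** **Inclusion rule.** Analysis of the Validity Outcomes estimates sensitivity, specificity, PPV and NPV in outpatients against a PCR-based test, with one restriction: "Home test results will only be included in this analysis if the test is performed within 24 hours of the time the swab" was taken.

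**Who is swabbed.** Recruitment describes two categories: i) "those receiving a CLIA certified nasal swab COVID-19 test at SHC at the moment of recruitment, and ii) those not". Under Test description, a participant with a positive SnapDx is "asked to take a CLIA nasal swab test at their nearest SHC testing site at their earliest opportunity". After a negative result, "then they will be asked to do nothing other than fill in a survey" and upload the image. The study also pays for an optional swab "when their SnapDx tests result or the saliva direct PCR test done by the lab shows a positive SARS-CoV-2 result".

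**Possible remedies.** The Rationale mentions randomly chosen negatives for estimating specificity, without a sampling fraction or weights; the validity analysis does not mention them. Handling of Missing Data plans multiple imputation in outpatients and gives unlinked PCR results as an example. It does not say whether tests that never had a swab are covered.

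**Reference and population.** The Validity section compares SnapDx with saliva direct PCR (PPA and NPA), on inpatient and outpatient samples run by five trained users. Analysis of the Validity Outcomes uses swab PCR in outpatients. Recruitment says "Feasibility and validity of the tests will be evaluated in the high-risk population", and Study Population defines that group as including "People from Bay area community and external sites with known positive saliva samples". None of these is named primary.

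**The concern.** This is partial verification. Tests paired with a swab at recruitment are safe, because that swab does not depend on SnapDx. For category ii participants, and for any daily test outside the window of the recruitment swab, a SnapDx positive (true or false) has a prompted route into the analysis. A SnapDx negative has none unless a laboratory saliva PCR is positive.

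False positives are then over-represented among the uninfected, so specificity is understated. True positives are over-represented among the infected, so sensitivity can be overstated. The saliva-PCR trigger can reduce the sensitivity bias, but only where a laboratory saliva sample exists.

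Sensitivity and specificity are the primary validity aim, and the Rationale ties the sensitivity calculation to FDA requirements. With reference and population also left open, the same data can give different primary results.

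**Working it through.** The plan states no expected accuracy, prevalence or swab uptake, so there is no figure of its own to reproduce. All rates below are assumptions.

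**Notation.** True sensitivity s = 80% and specificity sp = 95%. c = share of tests with an independent swab; p1 and p2 = infected share in tests with and without one (p1 = 10%). Among tests without one, u, r and w are the shares swabbed in time for SnapDx positives, uninfected SnapDx negatives and infected SnapDx negatives.

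With a = c(1−p1), b = (1−c)(1−p2), d = c·p1, e = (1−c)p2:

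- Crude specificity = sp(a+br) / [sp(a+br) + (1−sp)(a+bu)], below sp whenever r < u.
- Crude sensitivity = s(d+eu) / [s(d+eu) + (1−s)(d+ew)], above s whenever w < u.

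**Worked case.** Take 1500 tests, c = 50%, p2 = 10%, u = 100%, r = w = 0.

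- The 750 independently swabbed tests give TP 60, FN 15, FP 33.75, TN 641.25.
- The other 750 add only TP 60 and FP 33.75.
- Sensitivity = 120/135 = 88.9%; specificity = 641.25/708.75 = 90.5%.

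**Range** (p2 = 10% / 50% / 90%):

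| Crude specificity (true 95%) | Result, % |
|---|---|
| c=50%, u=100%, r=0 | 90.5 / 92.4 / 94.5 |
| c=50%, u=100%, r=10% | 91.3 / 92.8 / 94.5 |
| c=50%, u=100%, r=50% | 93.4 / 94.0 / 94.8 |
| c=50%, u=50%, r=0 | 92.7 / 93.7 / 94.7 |
| c=50%, u=r=50% | 95.0 / 95.0 / 95.0 |
| c=80%, u=100%, r=0 | 93.8 / 94.3 / 94.9 |
| c=20%, u=100%, r=0 | 79.2 / 85.5 / 92.9 |

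| Crude sensitivity (true 80%) | Result, % |
|---|---|
| c=50%, u=100%, w=0 | 88.9 / 96.0 / 97.6 |
| c=50%, u=100%, w=50% | 84.2 / 87.3 / 87.9 |
| c=50%, u=50%, w=0 | 85.7 / 93.3 / 95.7 |
| c=50%, u=w=100% | 80.0 / 80.0 / 80.0 |

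Higher prevalence in category ii shrinks the specificity loss and enlarges the sensitivity excess.

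**Predictive values.** PPV is unaffected at u = 100%. With r = w = 0, NPV describes category i only: 641.25/656.25 = 97.7%. If p2 = 50%, NPV over all tests is 997.5/1087.5 = 91.7%.

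**Do the plan's partial remedies remove the bias?** Assume true values of 85% and 95%, 25% independently swabbed and 80% uptake of prompted swabs. Positives are verified at 0.25 + 0.75×0.8 = 0.85 and negatives at 0.25.

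- No remedy: sensitivity 0.7225/0.76 = 95.1%; specificity 0.2375/0.28 = 84.8%.
- Adding 20% of the unswabbed negatives at random, unweighted (negatives verified at 0.40): 92.3% and 89.9%. The bias shrinks but remains.
- Adding the saliva-PCR trigger instead, assumed positive in 90% of infected and 1% of uninfected: 85.9% and 85.1%. The sensitivity bias nearly goes; the specificity bias stays.

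**Does weighting work?** Take 750 category ii tests, 10% infected, true values 80% and 95%, all SnapDx positives swabbed and 10% of negatives sampled at random.

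- No saliva PCR: crude 60/61.5 = 97.6% and 64.1/97.9 = 65.5%. Weighting on the SnapDx result recovers 80.0% and 95.0%.
- Saliva PCR positive in every missed infection, half of these swabbed because of it: 55% of missed infections are verified (0.5 + 0.5×0.1). Crude is 87.9% and 65.5%. Weighting on SnapDx alone gives 44.5% and 94.5%; weighting on both results recovers 80.0% and 95.0%.

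Both recoveries assume that swabbing depends on nothing else.

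**The case against.** The strongest reply is that few tests are exposed. Recruitment places validity in the high-risk group and adds the low-risk group for feasibility. Many high-risk participants are seeking testing, so they are a natural source of independent swabs, and deidentified, inactivated external samples cannot prompt one. Bags most likely hold only one or two tests, which limits repeat testing. Uptake of u = 100% is generous for a swab described as optional. At c = 90%, u = 50%, r = w = 0 and 10% infected throughout, the formulas give 80.9% and 94.7%, close to the truth. Finally, the Validity section's comparison runs saliva PCR on every sample and has no such selection.

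Much of this stands as a limit on size. With category ii 50% infected, that mild case still gives a sensitivity of 83.6%. None of it removes the mechanism: the validity analysis covers outpatients generally and excludes no result-triggered swab. The saliva comparison is a defence only if it is named primary, and it is not. Reading the populations together as high-risk outpatients is reasonable, but the plan does not say so, and the Validity section includes inpatients.

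**Conclusion.** The concern holds and should be fixed before analysis. As written, result-triggered swabs enter the primary accuracy analysis. The directions follow from the algebra: specificity falls if r < u and sensitivity rises if w < u. The specificity part is firmer, because the saliva-PCR trigger can offset the sensitivity part.

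The size cannot be derived from the documents. It is nil if only independent swabs enter, or if other SnapDx negatives are swabbed as often as other positives. It is several percentage points when half the tests lack an independent swab and uptake is strongly unequal, and larger still at c = 20%. The open choice of reference and population is plain from the text and needs no assumption.

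**What to change.** 1. Name one primary reference and one validity population, and reconcile Validity, Analysis of the Validity Outcomes and Recruitment.
2. Replace the 24-hour sentence with wording such as:

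   > Crude sensitivity, specificity, PPV and NPV will use only home tests within 24 hours of a swab ordered independently of the participant's SnapDx and study saliva-PCR results.

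   Identify these swabs from swab time, recruitment category and chart review. Compare swab time with the participant's first SnapDx or saliva-PCR result, because a swab triggered on day 1 can fall within 24 hours before the day-2 test. A yes/no field under Data Acquired would help but is optional.
3. Let result-triggered swabs and the random negatives enter only in a weighted analysis with the sampling fraction stated. Base weights on the SnapDx result and, where done, the laboratory saliva PCR; consider the per-test symptom survey.
4. State under Handling of Missing Data whether imputation covers tests never swabbed.

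**Cost.** Items 1, 2 and 4 are SAP wording. Item 2 leaves fewer tests, and its results describe people with independently ordered swabs; PPV and NPV still reflect the infected share in that set. If half of 1500 high-risk tests qualify (10% infected, assumed), the 95% Agresti–Coull intervals are:

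| | Half qualify | All verified |
|---|---|---|
| Sensitivity | 69.5–87.6% (60/75) | 72.8–85.7% (120/150) |
| Specificity | 93.0–96.4% (641/675) | 93.7–96.1% (1283/1350) |

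Item 3 can be imprecise. Among 750 category ii tests with 10% infected, there are 656.25 SnapDx negatives, of which 15 are infected. A 10% sample verifies about 1.5 of those infections, and the weighted sensitivity interval (delta method on the logit, no saliva PCR) is about 45–95%; a 50% sample gives about 65–89%. Weighting on saliva PCR needs a separate specimen for home tests, since "they will dispose of the tube in the trash"; the 120 on-site usability participants already give additional saliva. Without a specimen, weights rest on the SnapDx result and symptoms and assume swabbing depends on nothing else.

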### **Handling of Missing Data**

Although we have designed our study to minimize the amount of missing data, we expect to have a small amount of missing data. For example, hospitalized patients who are very sick or are discharged prior to day 5 may not provide data for days 1-5; participants may not complete the surveys each time they provide results from their home tests; or some PCR test results may not be able to be linked to the home test results. Analyses in the outpatient population will assume that data is missing at random and will use multiple imputation methods to account for the missing data. Given the small number of hospitalized patients expected, we will perform a complete case analysis in the analysis set consisting of hospitalized patients. Sensitivity analyses will be performed to evaluate the robustness of our findings to assumptions about missing data.

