### **Secondary Feasibility Outcomes:**

There are 4 secondary outcomes involved in assessing feasibility. These include

- 1) An indicator for ambiguous findings as measured by percent confidence (if < 80% confident) in interpretation of results by participant and by technician (ease of interpretation)
- 2) An indicator that the participant appropriately followed instructions for using the kit ( $\geq 80\%$  confident) (ease of use)
- 3) An indicator for whether participant called technical support and by reason (e.g., device leaked or there was a possible broken part) (ease of use)
- 4) An indicator by participant that the sample was sufficient and reached the indicated line for sample integrity (sample integrity)

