**Analysis of the Feasibility Outcomes**

Analyses of all feasibility outcomes will be performed in the outpatient analysis set.

The concordance of the test results will be compared to the results of PCR testing. We will calculate the proportion in agreement (# of tests where SnapDx and PCR testing agree/# total tests), the proportion correctly identified as positive (# of tests SnapDx-positive/# PCR-positive), and the proportion correctly identified as negative (# of tests SnapDx-negative/# PCR-negative). A threshold of 80% overall agreement and 85% agreement in the positive tests will indicate the home test is feasible.

Percent confidence in interpretation of the results and that instructions were followed correctly will be summarized as 1) percent of respondents stating that they are at least 80% confident in their interpretation and 2) median and interquartile range of reported confidence levels. Results will be reported separately for participants and technicians.

The proportion of participants who call technical support will be presented and the frequency of the reason for the call will be presented. The proportion of tests that have a sufficient amount of saliva to reach the indicator line will be presented.

The feasibility outcomes will be presented separately by demographic characteristics in a subgroup. For example, we will evaluate whether the concordance is comparable across different age groups, between men and women, etc.

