**Consent**

Potential participants will be approached by dedicated clinical research coordinators and study volunteers. They will be asked if they have an interest in participating and if so, whether they have an internet data-enabled cell phone capable of uploading high resolution photographs. Interested participants will then be directed to the digital e-consent implemented in REDCap on the mobile web browser. The CRC will be available to answer questions. The participants will also be provided an email and contact phone information for questions.

For the pediatric population, informed consent will be given by the legal guardian after they have been given the opportunity to answer any and all of the questions they may have and assent will be provided for children able to understand and complete the assent form (generally at least 7 years old).

Consent and Assent form will include a request to share access to their medical records for review of the results of any CLIA certified COVID test and any medical condition that might affect the veracity of testing. It will also include a request to observe the participants in-person or via video conferencing.

After consent, participants will receive a bag with materials for multiple home based tests as well as instructions on their phone via REDCap on how to use the test.

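### A home kit that is never finished cannot count against ease of use, so the secondary feasibility percentages for home tests can be overstated

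*Combined protocol and SAP*

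**What the plan says.** All feasibility outcomes are analysed in the outpatient set (Analysis of the Feasibility Outcomes). The secondary outcomes include confidence in interpretation and "An indicator that the participant appropriately followed instructions for using the kit", each cut at 80% confidence. The first summary is the "percent of respondents stating that they are at least 80% confident in their interpretation"; the second is a median and interquartile range of reported confidence levels. Instruction-following is summarised in the same way.

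Handling of Missing Data expects little to be missing ("we expect to have a small amount of missing data") and gives outpatient examples: "participants may not complete the surveys each time they provide results from their home tests", and PCR results that cannot be linked. It then sets one general rule: "Analyses in the outpatient population will assume that data is missing at random and will use multiple imputation methods". It closes with "Sensitivity analyses will be performed to evaluate the robustness of our findings to assumptions about missing data", without naming a method or scenario.

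On where testing happens, the text is mixed. Under Consent, "participants will receive a bag with materials for multiple home based tests", and Test Protocol asks for all of them to be used, most likely one or two. Usability/Feasibility instead has 120 people take one test each on site, and the Rationale speaks of self-testing at the research facility.

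**The concern.** In the Test description, the participant collects saliva, heats the tube, waits 40 minutes, reads the colour, photographs the tube and uploads the picture. The questionnaires come last. A person who stops at any earlier step never reaches the items that measure how easy the test was. Whether those items are missing can therefore depend on the difficulty they are meant to measure, which makes missing at random hard to defend for that group.

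Neither available treatment counts such a person as a failure. Taking respondents as the denominator omits them, and imputation under missing at random fills in values learned from finishers. The reported percentage then need not fall as abandonment rises. This matters because the Rationale states an aim of usability of home testing at scale, and the low-risk group is recruited to assess feasibility in the general population (Recruitment). The exclusion of people unable to operate the device, in both outpatient populations, pushes in the same favourable direction.

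**Working it through.** The documents give no completion rate, missing-data rate or expected confidence level, so there is no planned figure to reproduce. The check has two parts.

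**1. Trace an unfinished home kit through the plan.**

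- Primary feasibility outcome (participant versus technician reading of the photo): no photo, so no contribution.
- Confidence in interpretation and in following instructions: collected by a survey, one per test (Data Acquired), placed after the photo. The person is not a respondent, or is imputed.
- Technical support: "The proportion of participants who call technical support will be presented". This records the person only if they call.
- Saliva reaching the line: concerns sample volume, not whether the test was finished.
- No analysis has kits issued or tests started as its denominator.

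**2. Size the effect.** Let q be the favourable share among finishers (at least 80% confident) and m the share of issued home kits that are not finished. Both values are assumptions.

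- Respondent-only estimate: q.
- Imputation under missing at random: about q if the covariates carry little information. The symptom questionnaire also follows the photo, so for someone who finishes no kit the baseline demographics survey is the main source left.
- Every non-completion a failure: q(1 − m). Gap: qm.
- Half of non-completers true failures, the rest like finishers: q(1 − m) + qm/2 = q(1 − m/2). Gap: qm/2.

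With q = 0.85, in percent and percentage points:

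| m | Respondents | All fail: 0.85(1 − m) | Gap | Half fail: 0.85(1 − m/2) | Gap |
|---|---|---|---|---|---|
| 2% | 85 | 83.30 | 1.70 | 84.15 | 0.85 |
| 5% | 85 | 80.75 | 4.25 | 82.875 | 2.125 |
| 10% | 85 | 76.50 | 8.50 | 80.75 | 4.25 |
| 20% | 85 | 68.00 | 17.00 | 76.50 | 8.50 |

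With q = 0.90 and every non-completion a failure, the figures are 88.2%, 85.5%, 81.0% and 72.0%.

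A large sample does not remove the gap. For scale only, take 3000 kits, q = 0.85 and m = 10%, with the planned Agresti-Coull 95% intervals. Among respondents, 2295/2700 = 85.0% (83.6% to 86.3%). Over all kits, 2295/3000 = 76.5% (75.0% to 78.0%). The number 3000 is the two outpatient groups of 1500 each. It overstates the number of home kits, because it includes donors of external samples and people tested on site.

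**The case against.** The strongest reply is that the plan nowhere says how an unfinished test is handled. A reader might infer that it openly drops or imputes people who abandon the test; the documents do not say so. The outpatient examples are a survey skipped after a result was provided, which describes someone who finished, and an unlinked PCR result. That stands. But these are only examples, and the rule that follows covers outpatient analyses generally. Applied as written, it leaves no route by which an abandoned kit counts as a failure.

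Second, part of the testing is on site, and consent covers observation in person or by video. Silent abandonment is unlikely there, and donors of external samples run no test themselves. That stands too, and limits the point to tests taken away from the site.

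Third, a reader might infer that the respondents summary and the imputation rule contradict each other. One names a statistic and the other a general method, and imputed values could feed the statistic. The documents show loose wording rather than a contradiction: they do not say which rule governs.

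Fourth, a reader might infer that ease of use is overstated by a known amount, or that the feasibility decision is biased. Neither is supported. No non-completion rate is given, and at 2% the gap is 1.7 points or less with q = 0.85. Technical-support calls capture some failures. The 80%/85% threshold concerns agreement with PCR, not ease of use. The promised sensitivity analyses might help, but with no scenario stated they do not make non-completion count.

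Lastly, confidence in reading a result has no natural value for someone who never had one, and scoring it as not achieved mixes difficulty with forgetting or loss of interest. This is a fair reason to report completion in its own right and keep the respondent-only figure in view.

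**Conclusion.** The point holds for home tests and for the secondary ease-of-use indicators. Under the stated rules these indicators cannot register a kit that was issued or started but never finished, so they can be too favourable. If non-completion is counted as failure, the error runs in one direction only.

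Its size is unknown. Assuming 85% favourable among finishers and every non-completion a failure, it runs from 1.7 points at 2% non-completion to 17 points at 20%. It is half that if half of the non-completers are true failures. If missing data are as limited as the plan expects, the effect is small, but without a completion count a reader cannot tell. The primary feasibility outcome and the PCR agreement criterion do not rest on these figures. The change is worth making, but the point does not invalidate the study.

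**What to change.** 1. Log kits issued. For home tests, report completion (uploaded result divided by kits issued, first kit per person) as a feasibility result beside the technical-support proportion. Keep on-site tests separate and leave out donors of external samples.
2. Where no result was uploaded, do not impute confidence or instruction-following under missing at random. Report both indicators with non-completion counted as not achieved, beside the respondent-only figure.
3. Keep imputation under missing at random only for survey items left blank after a result was uploaded, and state that this rule governs the respondents summary in Analysis of the Feasibility Outcomes.

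The cost is mainly SAP wording. The documents describe REDCap consent, instructions and surveys but no kit log, so one must be set up if it does not already exist. The percentages will look less favourable, and some people who stopped for unrelated reasons will count as failures; showing both figures lets the reader judge this.

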**Analysis Sets:**

There are two key analysis sets that are subsets of the study population. The first subset consists of outpatients. The second subset consists of the patients hospitalized for COVID-related complications who will be tested daily for 5 days.

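### Hospitalised patients are expected to miss days because of their clinical course, yet the plan specifies complete case without defining the unit; if it means all five days, valid test pairs are lost

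*Combined protocol and SAP*

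**What the plan says.** Analysis Sets in the combined protocol and SAP names two key sets. One is outpatients. The other is the "patients hospitalized for COVID-related complications who will be tested daily for 5 days". Recruitment gives the second set its purpose: concordance between the CLIA test and the home saliva test "over a five day period when we expect to see a mix of positive and negative tests".

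Handling of Missing Data says "we expect to have a small amount of missing data" and gives as its first example that "hospitalized patients who are very sick or are discharged prior to day 5 may not provide data for days 1-5". For outpatients, "Analyses in the outpatient population will assume that data is missing at random and will use multiple imputation methods". For the other set, the rule is "we will perform a complete case analysis in the analysis set consisting of hospitalized patients", introduced by "Given the small number of hospitalized patients expected". The section closes with "Sensitivity analyses will be performed to evaluate the robustness of our findings to assumptions about missing data". No method or scenario is named for those sensitivity analyses, and the unit of a complete case is not defined.

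General Considerations prescribes 95% Agresti-Coull intervals. No estimator for hospitalised concordance is written down.

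**The concern.** Both reasons given for missing hospital data, severe illness and early discharge, are features of clinical course. Clinical course may plausibly relate to viral load, and so to how well SnapDx agrees with the reference. A method chosen for small sample size does not deal with that link. Small numbers argue for keeping every observed pair.

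These patients all enter with a positive PCR result (Criteria for Hospitalized Patients), so the negative results that Recruitment hopes to see must come later in their course. A patient who leaves on day 4 may have contributed three valid pairs. A rule requiring all five days would remove all three. What is at stake is the precision and representativeness of the five-day concordance in a group of 15 (Study Population) or 60 (Recruitment).

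**Working it through.** The documents give no dropout rate, missingness calculation or precision target for this set, so there is no planned figure to reproduce. All rates below are assumptions.

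**Inputs.** Five scheduled tests per patient (Analysis Sets). N = 15 (Study Population) or 60 (Recruitment). The stated total of 3060 equals 60 + 1500 + 1500, whereas 15 + 1500 + 1500 = 3015. Those sections need reconciling, but the percentages below do not depend on N. Assumed: day 1 is always observed, a constant fraction h of patients is lost per day afterwards, and every collected test has a reference result.

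**Tests lost under a patient-level rule.**
- Patients with all five days: (1−h)^4.
- Collected tests per patient: 1 + (1−h) + (1−h)^2 + (1−h)^3 + (1−h)^4.
- Share of collected tests discarded: 1 − 5(1−h)^4 / collected tests per patient.

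| h | All five days | Collected per patient | N = 15: collected / kept | N = 60: collected / kept | Discarded |
|---|---|---|---|---|---|
| 5% | 81.5% (12.2 of 15; 48.9 of 60) | 4.52 | 67.9 / 61.1 | 271.5 / 244.4 | 10.0% |
| 10% | 65.6% (9.8; 39.4) | 4.10 | 61.4 / 49.2 | 245.7 / 196.8 | 19.9% |
| 15% | 52.2% (7.8; 31.3) | 3.71 | 55.6 / 39.2 | 222.5 / 156.6 | 29.6% |

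At h = 20% the share discarded would be 39%. Under a test-level rule it is 0% at every h.

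**Precision.** If tests were independent, the standard error would grow by 1/√(1 − share discarded): 1/√0.900 = 1.05 at h = 5% and 1/√0.704 = 1.19 at h = 15%.

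**Possible bias.** Let d = 1 − (1−h)^4 be the share of patients who are incomplete, and let their agreement differ from that of completers by a fixed amount. Against the agreement that full five-day testing of everyone would show, the complete-case error is d × (completer agreement − non-completer agreement).
- Completers 15 points higher: 0.185 × 15 = 2.8 points at h = 5%, and 0.478 × 15 = 7.2 points at h = 15%. The estimate is too high.
- Completers 15 points lower: the same sizes, and the estimate is too low.
- No difference: no bias.
- Two groups in opposite directions, with completers at 80%, very sick patients at 90% and discharged patients at 70%. If 20% of patients fall in each lost group, the full value is 0.6 × 80 + 0.2 × 90 + 0.2 × 70 = 80%, so the bias is 0. With 10% very sick and 30% discharged, the full value is 78% and the bias is +2 points. With 30% and 10%, it is 82% and −2 points.

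**What using all pairs achieves.** The gap between the complete-case and all-available estimates is the share discarded × 15 points: 0.100 × 15 = 1.5 points at h = 5% and 0.296 × 15 = 4.4 at h = 15%. Of the 2.8 and 7.2 points, 1.3 and 2.7 therefore remain, because early leavers still contribute fewer tests. Bias is reduced, not removed.

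**The case against.** The strongest reply is that the plan never says a case means five days. The only agreement formula it contains, in Analysis of the Feasibility Outcomes, counts tests, although it is written for outpatients. On that unit a complete case is a test with both results, nothing is discarded, and the plan already matches the fix. This stands as a limit on the point: the loss is conditional. It does not dispose of it, because for a set defined by five daily tests the patient-level reading is the usual one, and the undefined unit lets either be chosen after the data are seen.

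Three further replies have some force. The plan expects little missing data, and eligibility favours patients likely to manage several days; both may limit loss, but the same plan still anticipates it. Sensitivity analyses are promised; as they are unspecified, they do not secure use of the partial patients' pairs. All feasibility analyses, the 80% and 85% agreement thresholds, and the sensitivity, specificity, PPV and NPV analyses use outpatients only, so no primary result depends on this set. That stands in full.

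Chance error may also outweigh the bias. At 90% agreement and N = 15, with 61.1 down to 39.2 tests kept, the simple 95% half-width 1.96 × √(0.9 × 0.1/n) is 7.5 to 9.4 points before any allowance for clustering. This is a fair caution about size, but it also argues against discarding pairs.

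A reader might infer that the concordance estimate is biased and that collected tests will certainly be thrown away. The documents support neither. They give no loss rates and no agreement by completion status, the two named reasons may pull in opposite directions, and the discard follows only under one reading of an undefined term.

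**Conclusion.** The concern holds in conditional form. The reason given for complete case does not answer the missingness that the plan itself describes. If the unit is the patient with all five days, about 10% to 30% of collected tests are discarded at an assumed 5% to 15% daily loss after day 1; if the unit is the test, none are. Under the patient-level reading the five-day concordance loses precision and is at risk of bias of unknown size and direction. The 2.8 to 7.2 points above rest on an assumed 15-point difference and serve only as illustration. The matter is confined to the hospitalised set and is worth correcting because the correction is cheap.

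**What to change.** In Handling of Missing Data, replace the complete-case rule for hospitalised patients with an analysis of every available SnapDx/reference pair, and state how a test is paired with its reference result. Report agreement by study day and overall. For the overall figure, use intervals that account for repeated tests per patient, by a patient-level bootstrap or a GEE with small-sample correction, in place of the plain Agresti-Coull interval, which treats tests as independent. Tabulate by day the number tested and the reason for loss (too ill, discharged, other). Keep five-day completers as a named sensitivity analysis, and specify at least one scenario in which agreement differs between patients who were lost and those who stayed.

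The cost is SAP wording and a little more analysis work, with no additional testing. The intervals will generally be wider than naive per-test ones, and bias from informative loss will be reduced but not removed; the report should say so.
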